4.3.1 Confirmatory analysis of secondary

Not applicable.

4.4 Exploratory analysis

4.4.1 Pre-injection and Post Injection SIAQ (version 2.1)

Descriptive analysis as detailed in Section 4.1 will be performed for each of the domain scores of Pre-Injection SIAQ (as administered at Visit 1) and of Post-injection SIAQ (as administered at Visit 1 and at Visit 8) in SS in order to assess participants' self-injection experience, including the perceived advantages and the potential limitations of self-injection of a sc medication.

Each domain score of both pre- and post-modules ranges from 0 to 10; scoring algorithm is presented in Section 6.7.1. Higher scores in each of the domains indicate a more positive self-injection experience, more confidence, higher satisfaction and less concerns with self-injections. Post-injection SIAQ domain scores, will be graphically illustrated at each scheduled visit.

Additionally, all individual items will be summarized by scheduled visit.

A by-subject listing of pre and post injection SIAQ will also be provided in SS.

4.4.2 Participant's Preference

The participants' treatment preference is assessed via a single question where only one answer should be selected.

Descriptive analyses for categorical data, as detailed in Section 4.1, will be used to analyze the participants' preference in SS.

4.4.3 Pharmacokinetics

The plasma concentrations of ZLP and its two major metabolites () will only be collected pre-dose on Day 1 (Visit 1) and Day 14 (Visit 8). The PK sample collected on Day 1 (Visit 1) will be representative of self-administered sc injection in either MG0011 or in commercial ZLP therapy. The PK sample collected on Day 14 (Visit 8) will be associated with self-administration using the ZLP-AI.

Summaries will be presented by scheduled day (visit) and by BMI category in the PK-PPS using n, arithmetic mean, median, SD, minimum, maximum, geometric mean, geometric coefficient of variation (geoCV) and 95% Confidence Interval (CI) (assuming log-normally distributed data). Three BMI categories will be defined based on tertiles derived from participants DV0013 baseline BMI values. Boxplots of ZLP plasma concentrations will also be presented by day (Visit 1, Visit 8) and by BMI tertiles. Summaries may also be prepared by scheduled day (visit) and study participant population (MG0011 or commercial supply), if needed.

Plasma concentration summaries will be based on observed values, with each sample falling within the time window as described below. The following rules will apply for PK data listings and summaries:

- Values below the lower limit of quantification Lower Limit of Quantification (LLOQ), will be reported as Below the Limit of Quantification (BLQ)
- Descriptive statistics of concentrations will be calculated if at least 2/3 of the individual data points at a timepoint are above the LLOQ. Values that are BLQ will be replaced by the numerical value of the LLOQ/2 in this instance.
- The 95% CI lower and 95% CI upper should be left blank if the SD (or equivalently, the geoCV) is 0.
- The geoCV will be calculated using the following formula where SD is the standard deviation from the log-transformed data:

$$\text{geoCV}(\%) = \sqrt{\exp(\text{SD}^2) - 1} \times 100.$$

Individual concentrations will be listed for the PK-PPS and will include the actual sampling time in days relative to the previous dose. The listing will include flags for concentrations that were

excluded from the summaries and figures, with the reason for exclusion.

Out of window/ exclusion rules for plasma concentration summaries and figures:

* A sample will be considered out of window relative to the current dose and will be excluded from the summaries and figures if the sample is collected after the dose administered at this visit.

* A sample will be considered out of window relative to the previous dose and will be excluded from the summaries and figures if the sample is collected <12 hours or >36 hours after the previous dose, and the sample was collected prior to the dose at that visit.

* Evidence that a dose(s) was missed, an incorrect dose(s) or less than the full dose(s) was administered 3 days prior to PK sampling.

* If the day immediately prior to the in-clinic Visit 8 (protocolled as Day 13) was administered by site personnel or care-giver, then the PK sample collected at Visit 8 will be listed and excluded from the summaries and figures.

4.5 Safety analysis

Safety endpoints are defined in [Table 1–1](#) and will be summarized descriptively in SS. Listings for all safety analyses will be presented.

4.5.1 Extent of exposure

IMP duration during the Intervention Period will be summarized in SS. The number of days on ZLP-AI use (IMP duration) will be calculated as follows:

$$\text{IMP duration} = [(\text{Date of Last Dose Received}) - (\text{Date of First Dose Received})] + 1$$

The exposure duration (i.e., total time at risk that incorporates 5 half-lives of ZLP) is defined as:

$$\text{Exposure duration (in days)} = [\min(\text{Last dose} + 40 \text{ days}, \text{Last Visit/Contact}) - (\text{Date of First Dose Received})] + 1$$

Note that temporary drug discontinuations and missed doses will not be incorporated into the calculations of the extent of drug exposure analysis.

All drug administration/exposure details will be listed.

4.5.2 Adverse events

Pre-existing conditions that are detected prior to the first self-injection of ZLP-AI will be considered as part of the medical history as recorded in the corresponding eCRF page.

For all participants, the Adverse Event reporting period starts with the signature of the ICF and will end with the last study visit or last contact (i.e., SFU, Visit 8).

Of note, for MG0011 patients, the ongoing AEs in the parent study will not be rolled over (and summarized or listed) in DV0013.

Adverse Events occurring after the first dose of ZLP back in MG0011 will be captured in MG0011 (thus not reported in DV0013) unless there is clear evidence that these are associated with the ZLP-AI and need to be captured in the DV0013 study.

Adverse Events occurring after the first dose of ZLP back on commercial supply will be captured through spontaneous reporting unless there is clear evidence that these are associated with the ZLP-AI and need to be captured in the DV0013 study.'

4.5.2.1 Data Definitions

Treatment Emergent Adverse Event (TEAE)

A TEAE is defined as an AE starting on or after the date/time of the first self-injection of ZLP-AI and up to and including 40 days after the final self-injection of ZLP-AI (or last contact depending on which occurs first). Adverse events starting before the date/time of the first self-injection of ZLP-AI will not be considered as TEAEs.

Adverse Device Event (ADE)

An ADE is an AE related to the use of the AI device ("Relationship to Study Device"= "Related" at the AE eCRF page).

An ADE includes:

- (1) Adverse events resulting from insufficiencies or inadequacies in the IFU, the deployment, the installation, the operation, or any malfunction of the device.
- (2) Adverse events as a result of a use error or intentional misuse of the investigational device.

Serious Adverse Device Event (SADE)

A SADE is an ADE that has any characteristics of a SAE.

Medication Errors

A medication error is an unintended failure in the drug treatment process that leads to, or has the potential to lead to, harm to the patient. A failure in the drug treatment process does not refer to lack of efficacy of the drug, rather to human- or process-mediated failures.

The medication error can be further classified based on the factual information on the case, into the following categories:

- **Medication errors associated with adverse reaction(s)**: result from an error (which has already occurred or accomplished) in the medication use associated with harm to the study participant.
- **Medication errors without harm**: result from an error (which has already occurred or accomplished) in the medication use associated with no harm to the study participant.
- **Intercepted medication errors (or near miss)**: in which an intervention (eg, the timely check of the incorrect preparation and administration of the study medication) has prevented actual harm being caused to the study participant.
- **Potential medication errors**: are the recognition of circumstances that could lead to a medication error, which may or may not involve a study participant.

The term potential medication error refers to all possible mistakes in the storing, preparation for administration, or administration of the IMP by the study participant and may lead to:

- A medication error with harm, but without knowing the actual cause,

- A medication error without harm and without knowing the actual cause,
- A medication error without harm but with the awareness of the actual cause.

4.5.2.2 Data Considerations for AEs

Where dates are missing or partially missing, AEs will be assumed to be treatment-emergent unless evidence exists that does not allow the AE to be treatment-emergent. Handling of missing dates for classification of AEs as TEAEs is described in Section 4.1.1.4.

AEs will be classified for severity according to the Common Terminology Criteria for Adverse Events (CTCAE) Version 5 or later (United States Department of Health and Human Services, Version 5.0, November 17, 2017). For any AEs where it is not possible to provide a CTCAE grading, the events will be assessed using a standard intensity classification (mild, moderate and severe). These will be tabulated together with the AEs that were not classified according to CTCAE criteria i.e., all Grade 1 AEs as per CTCAE criteria will be included in the 'mild' category together with those AEs classified as mild as per the 'standard' intensity classification.

The CTCAE displays Grades 1 through 5 with unique clinical descriptions of severity for each AE based on this general guideline:

- Grade 1 Mild; asymptomatic or mild symptoms; clinical or diagnostic observations only; intervention not indicated.
- Grade 2 Moderate; minimal, local or noninvasive intervention indicated; limiting age-appropriate instrumental activities of daily living.
- Note: instrumental activity of daily living refers to preparing meals, shopping for groceries or clothes, using the telephone, managing money, etc.
- Grade 3 Severe or medically significant but not immediately life-threatening; hospitalization or prolongation of hospitalization indicated; disabling; limiting self care activities of daily living.
- Note: self care activities of daily living refer to bathing, dressing and undressing, feeding self, using the toilet, taking medications, and not bedridden
- Grade 4 Life-threatening consequences; urgent intervention indicated.
- Grade 5 Death related to AE.

For the purpose of the tabulations AE intensity categories will be mapped to CTCAE severity classifications grade 1 to 5 as described below:

- Mild – Grade 1
- Moderate – Grade 2
- Severe – Grade 3, 4, 5, where
 - Grade 4 will be derived from the SAE monitoring form, when SAE is life threatening.
 - Grade 5 will be derived from the SAE monitoring form when SAE is fatal.

4.5.2.3 Adverse Events Summaries

AEs will be presented in Safety Set as “number of participants (percentage of participants) [number of events]”. In this style of output, “[number of events]” will include all cases of an AE including repeat occurrences in individual participants, while “number of participants” will count each participant only once.

1. A TEAE overview table will be provided including the number, percentage of participants and frequency of the following records:

- Any TEAE
- Serious TEAEs
- TEAEs Related to ZLP-AI (ADEs)
- Serious TEAEs Related to ZLP-AI (SADEs)
- Treatment-related TEAEs
- Severe TEAEs
- TEAEs leading to permanent withdrawal from study intervention.
- TEAEs Related to ZLP-AI (ADEs) leading to permanent withdrawal from study intervention.
- TEAEs leading to death
- All deaths (AEs leading to death)

A separate drug related AE overview table will be created.

2. The number, percentage of participants and frequency of the following TEAEs and/or ADEs will be summarized by MedDRA System Organ Class (SOC), high level term (HLT), and PT in separate outputs:

- Any TEAEs / ADEs
- Serious TEAEs / ADEs
- Non-serious TEAEs / ADEs
- Non-serious TEAEs above reporting threshold of 5% of participants
- TEAEs leading to permanent withdrawal from the intervention
- Serious ADEs that would preclude continued use of the ZLP-AI for self-administration (permanent withdrawal from the intervention)
- Treatment-related TEAEs leading to permanent withdrawal from the intervention
- TEAEs leading to death

3. The number, percentage of participants and the frequency of TEAEs and ADEs will be summarized by MedDRA SOC, HLT and PT for each of the intensity levels (mild, moderate and severe).

4. The number, percentage of participants and frequency of the following TEAEs will be summarized by relationship to treatment, SOC, HLT, and PT:
 - Any TEAEs
 - Serious TEAEs
 - Fatal TEAEs
5. The number and percentage of participants experiencing drug related TEAEs as well as serious drug related TEAEs (followed by the number of events) will be summarized by PTs.

For these summaries, the number and percentage of participants who experienced at least one TEAE (or ADE) as well as the number and percentage of participants who experienced each specific MedDRA SOC, HLT (if HLT is presented) and PT will be presented. For the presentation of TEAE incidences, the SOC will be sorted alphabetically, and HLT within SOC, and within HLT, the PT will be used and presented by decreasing total frequency.

All AE/ADE data will initially be listed in ScS. Separate listings in SS will display TEAEs or ADEs by category of interest.

4.5.2.4 AEs of Interest (AEIs)

The following are AEs of Interest (as defined in Section 6.8) that require separate statistical analyses:

- Infections
- Hypersensitivity reactions
- Anaphylactic reactions
- Malignancies or unspecified tumors

The number and percentage of participants who experience each AE of Interest will be summarized separately for each AEI. The following summaries will be presented:

- Incidence of AEIs and serious AEIs by SOC and PT (serious and non-serious will appear in the same table)
- Incidence of AEIs by relationship, SOC and PT
- Incidence of AEIs by maximum intensity (mild, moderate and severe), SOC and PT.

A detailed by participant listing will be created showing all the information related to the above-mentioned AEs.

4.5.2.5 AEs of Special Monitoring

Neisseria meningitidis infection is considered as part of AEs of special monitoring. Such cases will be identified through the HLT “Neisseria infections” and will be captured in the overall AE output.

4.5.3 Tolerability - Injection Site Reactions and Medication Errors

Injection Site Reactions

An AE reported in the eCRF with a start date/time on or following to the first self-administration of ZLP AI through the final self-injection and until the safety follow up which is coded into MedDRA High Level Terms of “Administration site reactions NEC” or “Injection site reactions” will be evaluated as Injection Site Reaction (ISR). ISRs will be summarized in SS overall, by intensity and by seriousness. Summaries will be based on the number and percentage of participants who experienced at least one ISR event by MedDRA SOC, HLT and PT followed by the number or ISR events.

A separate assessment of tolerability at injection site (as part of physical examination and as defined in the study protocol) is performed during the on- site visits assessing pain, burning, erythema, itching, swelling and bruising based on a Likert type scale of 0 to 3. Greater grade indicates more severe injection site reaction. For each of the assessments a shift table will be created to show the shift of injection site reaction grading from Visit 1 to Visit 8.

ISR and tolerability data will be listed in SS.

Medication Errors

An adverse reaction is a response to a medicinal product which is noxious and unintended (Directive 2001/83/EC, Article 1 (11)). An adverse event which is reported as a consequence of a medication error is considered as an adverse reaction.

Participants with medication errors associated with adverse reactions will be identified via the eCRF- Adverse Event form as reported by the investigator. The number and proportion of participants experiencing such AEs during the Intervention Period will be summarized by MedDRA SOC, HLT and PT in SS. A by-participant listing in SS will also be created listing all the AEs associated with medications errors reported in the study.

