## Overall design

DV0013 is a Phase 3b, multicenter, open-label study to evaluate the safe and effective use of a ZLP-AI combination product for sc self-administration of ZLP solution (the IMP) by study participants with generalized myasthenia gravis (gMG), planned to be conducted in Europe and the US.

The study will aim to reflect real-world use scenarios by including participants who are already self-administering ZLP using the PFS on a once-daily dosing regimen as part of the MG0011 long-term open-label extension (OLE) study or who are on commercial ZLP treatment for at least 1 month prior to Screening.

DV0013 will consist of 9 visits (2 clinic visits and 7 remote telephone visits) and 14 self-administrations using the ZLP-AI.

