1.2 Schema

Figure 1-1: Study schematic

AI=auto-injector; SFU=Safety Follow-Up

Note: \*=Participants roll back into MG0011 or go back to self-administration with commercial supply on the next day after Visit 8.

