**Table 1-1: Schedule of study assessments**

Period	Screening Period	Treatment Period								EW b (In-clinic)	SFU Visit c (Phone call)
Name	Screening (In-clinic)	Day 1 (In-clinic)	Day 2 (Phone call) a	Day 4 (Phone call) a	Day 6 (Phone call) a	Day 8 (Phone call) a	Day 10 (Phone call) a	Day 12 (Phone call) a	Day 14 (In-clinic)		
Visit #	1		2	3	4	5	6	7	8	9	
Day	1		2	4	6	8	10	12	14	(Final dose +7±3 days)	
Participant completes postinjection SIAQ (SIAQ POST module) j		X							X		
Study personnel collect ZLP-AI devices from each participant to send to UCB for structural/mechanical integrity assessment t m		X							X		
Drug and device accountability									X		
Record TEAEs, SAEs, ADEs, SAEs, medication errors, ISR, and device deficiencies n		X	X	X	X	X	X	X	X	X	
Blood sampling for ZLP plasma concentrations o	CCI										

ADE=adverse device effect; AE=adverse event; AI=auto-injector; βHCG=beta human chorionic gonadotropin; C-SSRS=Columbia-Suicide Severity Rating Scale; EW=early withdrawal; IMP=investigational medicinal product; ISR=injection site reaction; IXRS=interactive response technology;

MGFA=Myasthenia Gravis Foundation of America; PK=pharmacokinetic; SAE=serious adverse device event; SAE=serious adverse event; SFU=Safety

Follow-Up; SIAQ=Self-Injection Assessment Questionnaire; ZLP=zilucoplan

a Telephone visits which would be scheduled to occur on a weekend day may be skipped, and the data for the respective days (Saturday and Sunday) will be collected on the next clinic business day (Monday).

b If a study participant permanently withdraws from the study, the study participant should return to the clinic for an EW Visit as soon as possible but no later than the next scheduled in-clinic visit.

c Study participant will be required to perform a SFU telephone call 7 days (±3 days) after their final study dose of ZLP using the ZLP-AI.

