j The preinjection SIAQ (SIAQ PRE module version 2.1) will be completed preinjection at Visit 1; the postinjection SIAQ (SIAQ POST module version 2.1) will be completed directly following self-injection and no later than 30 minutes postinjection at Visit 1 and Visit 8 during the study Treatment Period.

k In accordance with the draft Food and Drug Administration Suicidal Ideation and Behavior Prospective Assessment of Occurrence in Clinical Trials

l Guidance (Food and Drug Administration, Guidance for Industry, 2012) study participants will be asked to complete the C-SSRS at study visits as specified.

m At Visits 1 and 8, the Investigator will observe the participant self-administering with the ZLP-AI device. The used ZLP-AI devices will be visually inspected by the Investigator to determine if the entire dose was completely delivered (ie, the yellow plunger that can be seen through the device window is completely depressed).

n All used AI devices will be sent to UCB for assessment of structural and mechanical integrity and damage (ie, clear evidence of damage/compromised structural integrity—not superficial, cosmetic imperfections).

o Note that ADEs, SAEs, ISRs, and medication errors can only be recorded on the 14 days that the participant is using the ZLP-AI, and device deficiencies will also be collected during those 14 days. Device deficiencies will be reported via the eCRF. In addition, sites will fill out a product quality complaint form; all product quality complaints will be investigated by UCB.

p A single PK sample will be collected **CC1**.

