#### **Safety Follow-Up Visit**

- Visit 9: For all participants, an SFU via telephone call, 7 days ( $\pm 3$  days) after their final study dose using the ZLP-AI, will be required. Any AEs, SAEs, ADEs, or SADEs will be recorded. Participants who were enrolled into DV0013 from MG0011 will roll back into MG0011 on the next day following Visit 8 and will continue to be followed up as part of the MG0011 protocol. Participants who were enrolled following treatment with commercial ZLP treatment will continue with their prescribed treatment; for AEs occurring after the SFU telephone call and up to 40 days after the last administration, participants will be instructed to contact the site or follow the safety reporting according to the label.

The study duration for each participant will be approximately 21 days.

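### The documents disagree on whether injection-site events after the return to the prefilled syringe belong in the ZLP-AI injection-site-reaction count, and SAP 4.5.3 has no filter to settle it

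*SAP*

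**What the plan says.** **The counting rule.** SAP 4.5.3 takes as an ISR "An AE reported in the eCRF with a start date/time on or following to the first self-administration of ZLP AI" and "through the final self-injection and until the safety follow up which is coded into MedDRA High Level Terms", the two groups being administration-site and injection-site reactions. It does not ask which device gave the injection. SAP Table 1-1 places ISR occurrence under the objective on safety and tolerability of ZLP-AI self-administration, as an 'other' safety endpoint.

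**What happens after Visit 8.** Protocol 1.2 states: "Participants roll back into MG0011 or go back to self-administration with commercial supply on the next day after Visit 8". The Overall design section describes these participants as "already self-administering ZLP using the PFS on a once-daily dosing regimen", so daily syringe injections resume. Table 1-1 requires participants to "perform a SFU telephone call 7 days (±3 days) after their final study dose of ZLP using the ZLP-AI".

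**Text that lets later events in.** For the SFU call, Protocol 4.1 says: "Any AEs, SAEs, ADEs, or SADEs will be recorded". For commercial-supply participants it points to the site or to label reporting only for events after that call. Protocol 8.3.1 collects all adverse events from consent to the SFU and requires eCRF entry, post-treatment periods included.

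**Text that keeps them out.** SAP 4.5.2 says "Adverse Events occurring after the first dose of ZLP back in MG0011 will be captured in MG0011 (thus not reported in DV0013") and sends the corresponding commercial-supply events to spontaneous reporting. Both routes have one exception: clear evidence linking the event to the auto-injector. Separately, a Table 1-1 footnote says "ISRs, and medication errors can only be recorded on the 14 days that the participant is using the ZLP-AI".

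**The concern.** An ISR is local to one injection, so a reaction at a syringe site says nothing about the auto-injector.

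Take a commercial-supply participant who has no reaction on Days 1 to 14, bruises after a syringe injection on Day 17 and mentions it at the SFU call. Under Protocol 4.1 and 8.3.1 the bruise is entered in the DV0013 eCRF and, if coded to either MedDRA group, SAP 4.5.3 counts it. Under SAP 4.5.2 it goes to spontaneous reporting. Under the Table 1-1 footnote it is not recorded as an ISR at all.

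The reported ISR frequency would then depend on which text each site followed, on the date of the SFU call and on the entry route. MG0011 participants' events probably go to MG0011, so any addition would come mainly from commercial-supply participants. A pooled percentage would hide that.

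**Working it through.** **Inputs.** 14 auto-injector doses per participant, at least 25 participants and about 350 administrations (Protocol 9.8 and Overall design); SFU at final dose + 7 ± 3 days (Table 1-1); return to previous supply at final dose + 1 (Protocol 1.2); once-daily dosing (Overall design).

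**The plan's own figure.** 25 × 14 = 350, which agrees with the stated total.

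**Syringe injections in the SAP 4.5.3 window.** For a call s days after the last auto-injector dose, the number is s if that day's dose comes before the call and s − 1 if it comes after. Share of injections = k/(14 + k). Event increase = k/14.

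| SFU call | Syringe injections k | Share of injections in window | Event increase |
|---|---|---|---|
| + 4 days (Day 18) | 3 to 4 | 3/17 = 18% to 4/18 = 22% | 21% to 29% |
| + 7 days (Day 21) | 6 to 7 | 6/20 = 30% to 7/21 = 33% | 43% to 50% |
| + 10 days (Day 24) | 9 to 10 | 9/23 = 39% to 10/24 = 42% | 64% to 71% |

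For 25 completers this is 75 to 250 syringe injections (25 × 3 to 25 × 10) against 350 by auto-injector.

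The last column assumes that every syringe reaction is entered and that both devices carry the same risk per injection. If the call-day dose precedes the call, the increase is 29% to 71% (nominal 50%).

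**Participant incidence.** The documents give no ISR risk, so I assume p = 0.5%, 1% or 2% per injection and independence between injections. Then 1 − (1 − p)^k gives 6.8%, 13.1% or 24.6% for 14 injections, and 10.0%, 19.0% or 34.6% for 21.

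**With the restrictive text applied.** Under SAP 4.5.2, no syringe injection feeds the table without clear evidence of an auto-injector link. The footnote, read alone, also gives 0.

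**The passages side by side.**

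| Text | Post-Visit 8 syringe reaction |
|---|---|
| Protocol 4.1 (Visit 9) and 8.3.1 | Entered in the DV0013 eCRF |
| SAP 4.5.3 | Counted if entered and coded to either group |
| Protocol 9.4.2 | Within the treatment-emergent period (40 days after the final dose or last contact, whichever is first) |
| SAP 4.5.2 | Not reported in DV0013 unless clearly linked to ZLP-AI |
| Table 1-1 footnote | ISR not recorded |

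The footnote's 14-day limit also covers ADEs, which the Visit 9 text says are recorded at the call. Those two passages conflict on that item as well.

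**The case against.** The strongest reply is that SAP 4.5.3 only selects from events already in the eCRF, and SAP 4.5.2, in the same safety section, says what gets there. Its exception for a clear auto-injector link is a device condition. On that reading the Day 17 bruise never reaches the table, and the footnote leads to the same place. Running the window to the SFU also has a proper use: it keeps late reactions to the last auto-injector doses. Device-related injection-site terms appear separately in the ADE tables (SAP 4.5.2.1 and 4.5.2.3), and the graded injection-site assessments at Visits 1 and 8 precede the return to the syringe.

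Much of this stands. The plan, read as a whole, does not direct anyone to count syringe reactions as auto-injector reactions.

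It does not remove the disagreement, for three reasons. First, SAP 4.5.2 describes where events are captured; it is not a filter on the ISR tables. Sites work from the protocol, which tells them to enter events up to the SFU. Second, SAP Table 4-1 does not list the carve-out as a change from the protocol, and for commercial-supply participants it contradicts Protocol 4.1 directly. Third, the footnote limits what is recorded as an ISR, whereas SAP 4.5.3 derives ISRs from MedDRA coding. A bruise entered as an ordinary adverse event would still be picked up.

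**Conclusion.** The documents give incompatible answers for injection-site events between the first syringe dose and the SFU call, and the ISR rule has no condition of its own that would make the answer irrelevant. The possible effect runs from near zero, where SAP 4.5.2 is applied, to the tabulated increases, which are upper bounds resting on full recording and equal risk per injection. The counts are for completers with 14 auto-injector doses; the incidence figures also rest on assumed risks and independence.

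A reader might infer that the SAP counts syringe reactions as auto-injector reactions and so overstates the device's ISR rate by 29% to 71%. The documents do not support that. SAP 4.5.2 and the footnote both exclude such events, and those figures describe sites that follow only the protocol's general text.

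This is a minor point. The study is single-arm and descriptive, and no test or decision rule depends on ISR occurrence.

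**What to change.** In SAP 4.5.3, restrict the ZLP-AI ISR tables to events in the two MedDRA groups with onset from the first auto-injector dose and before the first post-study syringe dose, plus any later event whose relationship to the study device is recorded as related. The documents do not say that the date of the first dose back is collected. If it is not, use onset up to the day of the last ZLP-AI dose. List other injection-site events up to the SFU separately, as occurring after the return to the syringe.

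Reconcile the Table 1-1 footnote, Protocol 4.1 (Visit 9), 8.3.1 and 9.4.2, and SAP 4.5.2 and 4.5.3 to one rule, and add any remaining departure from the protocol to SAP Table 4-1.

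The analysis change costs one SAP sentence, one filter and one listing. The device-relationship item is already on the adverse event form (SAP 4.5.2.1), and no visit is added. The protocol wording needs a clarification to sites or can be carried in the next amendment. With the fallback date, a reaction starting on the morning after the last auto-injector dose moves to the separate listing unless it is recorded as device-related; nothing is lost from the report.
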